### **8.5.3 Analysis of the Secondary Variables**

Each secondary endpoint will be analyzed individually, and no multiplicity control will be applied. Analyses of secondary variables will not account for missing values.

The secondary endpoint of clinically significant arrhythmia events will be analyzed similarly to the primary endpoint.

The secondary endpoint of a total duration of clinically significant arrhythmia events will be analyzed by a linear mixed model. Details of the model specifications will be in the SAP

The secondary endpoint of risk of outside K+ safe range will be analyzed with a similar approach of the primary endpoint but with a logit link function. Details of the model specification will be included in the SAP.

A nominal p-value and a 95% C.I. of the effect between two treatment groups will be reported for each of secondary endpoints.

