### 5.1.3 Potassium Measurements

A further secondary objective of the study (see [Section 2.2](#)) is to determine whether the addition of oral sodium zirconium cyclosilicate (Lokelma®) during the 2-month treatment phase with the 3.0 K+/2.5 Ca++ dialysate bath will reduce the number of days outside the “K+ safety range” of 4.0 to 5.5 mEq/L compared to the 2-month treatment phase with the 2.0 K+/2.5 Ca++ dialysate bath.

K+ Piccolo POCT will be performed weekly during the two 8-week Treatment phases, as follows: pre-dialysis, and promptly before dialysis termination and 30 minutes prior to rinse back (along with Ca++ and PO4 measurements); see [Section 4.2.1](#).

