## 7.2 Dose and Treatment Regimens

### 7.2.1 Dosing Regimen

Patients will take Lokelma supplementation on off-dialysis days (4 days/week) while receiving hemodialysis with 3.0 K+/2.5 Ca++ mEq dialysate bath (8-week treatment phase):

- Patients on a Monday-Wednesday-Friday dialysis schedule will take the study drug on Tuesday, Thursday, Saturday, and Sunday
- Patients on a Tuesday-Thursday-Saturday dialysis schedule will take the study drug on Monday, Wednesday, Friday, and Sunday.

The individual starting dose will be 5.0 grams (4 days/week), and will be titrated weekly in 5.0 gram increments up to a maximum of 15.0 grams (4 days/week) to maintain K+ within the desired target range (between 4.0 and 5.5 mEq/L):

- Patients who fail to achieve a pre-dialysis K+ of  $\leq 5.5$  mEq/L after one week of 5.0 grams Lokelma will be treated with 10.0 grams on off-dialysis days for an additional 7 days.
- Patients failing to achieve a pre-dialysis K+ of  $\leq 5.5$  mEq/L after one week of 10.0 grams Lokelma will have their study drug dose increased to 15.0 grams.
- Patients failing to achieve the target K+ after a 7-day course of 15.0 grams Lokelma on off-dialysis days will be considered a treatment failure and withdrawn from the study.

Potassium levels will be regularly monitored throughout the 8-week treatment phase, and the study drug dose adjusted based on the potassium levels (i.e., increased [up to a maximum of 15.0 grams/day] if potassium is  $>5.5$  mEq/L, or decreased if potassium is  $<4.0$  mEq/L).

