#### **8.4.3 Secondary Efficacy Endpoint #2: Events Outside the Optimal K+ “Window”**

The number of events of K+ outside of the 4.0 to 5.5 mEq/L safety range is a secondary efficacy endpoint in this study, The total number of events of pre- or post-dialysis K+ falling outside the “K+ safety range” will be averaged and compared between the two dialysate groups.

The study aims to show that patients experience less risk of K+ falling outside the range of 4.0 to 5.5 mEq/L while receiving experimental compared to standard treatment.

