### **8.5.2 Analysis of the Primary Variable**

The primary efficacy endpoint is the frequency of atrial fibrillation events occurring during the 8-week Treatment Phase-1 and the 8-week Treatment Phase-2 dialysate cross-over periods.

The primary analysis will test the null hypothesis that there is no difference in the rate of atrial fibrillation events between the 3.0K+ dialysate bath with Lokelma and the 2.0K+ dialysate bath without Lokelma, against the alternative hypothesis that there is a difference in the rate of atrial fibrillation events between the 3.0K+ dialysate bath with Lokelma and the 2.0K+ dialysate bath without Lokelma. Statistical hypothesis testing will be completed at a 2-sided 0.05 significance level.

The primary analysis will not account for missing values. However, sensitivity analyses will be conducted using the pattern mixture model with multiple imputation (PM-MI) method. Details of the PM-MI method will be provided in the SAP.

A generalized linear model assuming the distribution of negative binomial will be used, with fixed effect terms for the treatment groups (3.0K+ dialysate bath with Lokelma and 2.0K+ dialysate bath without Lokelma), the study period, and log (the duration of period) as an offset variable. An unstructured working variance-covariance will be employed. Additional model terms may be included, details of which will be described in the SAP. The estimated risk ratio between groups and its 95% robust confidence interval (CI) will be displayed. The null hypothesis will be rejected if the p-value (based upon the Wald statistics) is less than 0.05.

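### The potassium-window analysis ignores missing weeks, while Section 7.2.1 withdraws patients on the experimental treatment only for missing the same potassium target, so out-of-range risk on 3.0 K+ is understated

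*Protocol*

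**What the plan says.** Secondary endpoint #2 concerns weekly potassium outside 4.0 to 5.5 mEq/L, before or at the end of dialysis. Section 8.4.3 gives the aim: "The study aims to show that patients experience less risk of" potassium leaving that range "while receiving experimental compared to standard treatment". Under Section 5.1.3, "Piccolo POCT will be performed weekly during the two 8-week Treatment phases", which gives 8 scheduled readings of each kind per phase.

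Section 8.5.3 says this endpoint "will be analyzed with a similar approach of the primary endpoint but with a logit link function", leaves the model details to the SAP, and fixes the missing-data rule itself: "Analyses of secondary variables will not account for missing values". Section 8.5.2 also leaves missing values out of the main analysis of the primary endpoint, but adds that "sensitivity analyses will be conducted using the pattern mixture model with multiple imputation (PM-MI) method". Section 8.5.3 adds nothing comparable.

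Section 7.2.1 titrates Lokelma weekly to keep potassium "within the desired target range (between 4.0 and 5.5 mEq/L"), in steps of 5, 10 and 15 grams. A patient who misses the target "after a 7-day course of 15.0 grams Lokelma on off-dialysis days will be considered a treatment failure and withdrawn from the study".

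Section 3.9 reads differently. It lists potassium above 6.5 mEq/L at 15 grams as a reason to stop the investigational product, and it keeps visits and data collection going to study completion unless the patient withdraws consent.

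Section 8.5.1 refers to each endpoint's section for the handling of intercurrent events, but 8.5.3 contains none. Its list of causes of missing data does not name withdrawal for treatment failure.

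**The concern.** The event that defines a bad result on this endpoint is also, under Section 7.2.1, the event that ends observation. It does so on one treatment only. The 2.0 K+ period has no matching rule; the nearest text is a note in Section 3.9 about potassium above 6.5 mEq/L, which falls under stopping the investigational product.

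The primary model is a marginal one with a working covariance and robust intervals, and the potassium model is to resemble it. Unweighted, such a model generally needs missingness to be unrelated to the outcome. Here a measured potassium value causes the missingness.

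Failures are plausible. Patients enter with pre-dialysis potassium of 5.1 to 6.5 mEq/L and move to a higher-potassium bath, and Section 1.1.1 calls it unclear whether Lokelma achieves the same control there. This endpoint is the trial's formal efficacy comparison of potassium control on the two treatments, so a distortion here affects a question the trial sets out to answer.

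**Working it through.** The protocol states no figure for this endpoint. The planned 88 patients are derived for atrial fibrillation and are not affected.

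**Step 1. Weeks kept by a persistent failure**

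- *Dosing from Day 1* (the synopsis and Table 1 place Lokelma in the accommodation weeks): 5 g on Day 1, 10 g on Day 8, 15 g on Day 15, failure seen on Day 22. Treatment Phase 1 starts on Day 15, so the readings of Days 15 and 22 remain: 2 of 8.
- *Dosing from Week 3* (Sections 7.2.1 and 7.5 speak of the 8-week phase): 5 g on Day 15, 10 g on Day 22, 15 g on Day 29, failure seen on Day 36. Four of 8 readings remain.
- The same patient on 2.0 K+ supplies 8 of 8 when that treatment comes first (Sequence A as labelled in Section 3.5). If 3.0 K+ comes first (Sequence B), withdrawal also removes the whole 2.0 K+ period.

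**Step 2. Inputs assumed, not in the documents**

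Non-failures are out of range in 30% of weeks on both baths. Failures are out of range in 90% of weeks on 3.0 K+. The failure share f is 15%, also shown at 10% and 20%. Let k be the weeks kept.

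Observed 3.0 K+ risk = [(1−f)·8·0.30 + f·k·0.90] / [(1−f)·8 + f·k]. At f = 0.15:

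- True risk: 0.85·0.30 + 0.15·0.90 = 0.39
- k = 2: (2.04 + 0.27)/(6.8 + 0.3) = 0.325
- k = 4: (2.04 + 0.54)/(6.8 + 0.6) = 0.349

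**Step 3. Failures worse on 3.0 K+ only (2.0 K+ risk 0.30)**

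- True OR: (0.39/0.61)/(0.30/0.70) = 1.49
- Observed OR, k = 2: (0.325/0.675)/(0.30/0.70) = 1.13 (1.125 unrounded)
- Observed OR, k = 4: (0.349/0.651)/(0.30/0.70) = 1.25

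For f of 10, 15 and 20%, true ORs of 1.31, 1.49 and 1.69 appear as 1.08, 1.13 and 1.18 when k = 2.

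**Step 4. Failures equally out of range on both baths (true OR 1.00)**

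Half the failures lose all 8 of their 2.0 K+ weeks. Observed 2.0 K+ risk = (2.04 + 0.075·8·0.90)/(6.8 + 0.075·8) = 2.58/7.4 = 0.349.

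- k = 2: OR = (0.325/0.675)/(0.349/0.651) = 0.90; it is 0.93 and 0.87 at f = 10% and 20%, and 0.97 at 5%
- k = 4: both treatments lose half of the failures' weeks, so OR = 1.00

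With 60% of weeks out of range in the background, the k = 2 values are 0.97, 0.95 and 0.94 for f of 10, 15 and 20%. A period term shifts these expected values only in the second decimal.

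**Step 5. Simulation with no true difference**

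200,000 patients per scenario. Assumptions: mean pre-dialysis potassium 4.8 to 5.2 mEq/L; between/within-patient SD 0.5/0.5 or 0.6/0.3; correlation of patient means between treatments 0, 0.5 or 1; no effect of dose steps on potassium; pre-dialysis readings only; withdrawal as in 7.2.1.

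| Analysis | Observed OR (truth 1.00) |
|---|---|
| Observed weeks, dosing from Day 1 | 0.55 to 0.99 |
| Observed weeks, dosing from Week 3 | 0.73 to 1.13 |
| Follow-up continues after failure | 0.99 to 1.01 |
| Post-failure weeks counted as out of range | 1.07 to 2.01 |

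Experimental risk was understated in every scenario, for example 0.364 seen as 0.240, or 0.291 seen as 0.279. Simulated withdrawal ran from about 17% to 49%, above the 10% non-completion the protocol expects, so these are wide bounds and not forecasts.

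**The case against.** The strongest objection is Section 3.9. If it governs, visits and potassium readings continue after Lokelma is stopped, and the null simulation returns to about 1.00. This stands as a condition on the point but does not remove it, because Section 7.2.1 says in plain terms that the patient leaves the study and the protocol does not say which section prevails.

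A reader might infer that the odds ratio is always biased toward the experimental treatment. That is not supported. Failures who start on 3.0 K+ also lose their 2.0 K+ period, which offsets part or all of the bias, and the null simulation reaches 1.13.

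A reader might also infer that true loss of control could be reported as benefit. The arithmetic does not show this: in the true-harm scenario the estimates stay above 1 (1.08 to 1.18). Values below 1 arise where control is equal. Nor do failures disappear altogether, since readings up to and including the failing visit stay in.

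The inputs have no documentary basis. The 10% expected non-completion covers all causes, so 15% or 20% for this cause alone may be high. The titration steps are triggered by high pre-dialysis potassium, so nothing shows that the lost end-of-dialysis readings would have been out of range. These limits bear on size, not on the mechanism.

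Finally, the SAP could add an analysis. It could, but the protocol has already fixed the missing-data rule for the secondary endpoints and not merely deferred it.

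**Conclusion.** The point holds in a limited form. If Section 7.2.1 is followed as written, the experimental out-of-range risk is understated, because a persistent failure supplies 2 to 4 of 8 weeks. A true excess on 3.0 K+ is attenuated: under the assumed 30%, 90% and 15%, from 1.49 to between 1.13 and 1.25. With equal control, the odds ratio is about 0.87 to 0.97 with dosing from Day 1 (failure shares of 5 to 20%) and close to 1.00 with dosing from Week 3 in the same calculation. A tilt toward the experimental treatment is therefore usual, not certain. Both the size and the existence of the effect depend on how the conflict between Sections 3.9 and 7.2.1 is settled.

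This should be fixed, but it is not critical: the endpoint is secondary, its p-value is nominal, and the primary analysis is not touched by this point.

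**What to change.** 1. The sponsor reconciles Sections 3.9 and 7.2.1, including the potassium threshold and whether weekly potassium data are still collected after treatment failure. Which clinical rule applies is for the sponsor; this review proposes none.
2. In Section 8.5.3, for secondary endpoint #2, replace the unqualified missing-data sentence with an extension of the pattern-mixture multiple-imputation sensitivity analysis to the weekly binary potassium outcome, with treatment-failure withdrawal as its own missingness pattern. The plan for the primary count endpoint cannot simply be reused; the binary version needs its own specification.
3. Report the number and timing of treatment failures by sequence beside the result.
4. Show the analysis that counts post-failure weeks as out of range only as a bounding sensitivity analysis, and state whether it applies to the pre-dialysis or the end-of-dialysis reading.

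Item 4 should not become the main analysis. In the equal-control scenario of Step 4 with k = 2, it gives 1.17 to 1.33 for failure shares of 10 to 20%. At 15%: (2.04 + 0.27 + 0.15·6)/8 = 0.401 against 0.349, an OR of 1.25 where the truth is 1.00. In simulations of 88 patients it rejected a true null in about 25, 45 and 65% of runs at 10, 15 and 20% failures, against about 9, 13 and 16% for the planned analysis.

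The cost is a wording change, one imputation specification and two extra runs. If weekly readings continue after failure, items 2 and 4 matter much less.

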#### **8.5.4 Analysis of the Exploratory Variables**

All exploratory endpoints will be analysed using the FAS. A full description of the exploratory endpoints and analyses will be included in the SAP.

#### **8.5.5 Subgroup analysis**

The primary and select secondary variables may be analyzed based on the following pre-defined subgroups:

1) ESRD patients with diabetes mellitus:

Patients with diabetic nephropathy as their proximate cause of ESRD will be pre-identified as a group of patients with increased risk for post-dialysis atrial fibrillation.

2) ESRD patients with a prior history of atrial fibrillation:

Patients with a history of atrial fibrillation but in stable sinus rhythm will be pre-identified as a group with increased risk for post-dialysis atrial fibrillation.

3) ESRD Patients with grade II or higher levels of diastolic dysfunction

Patients with echocardiogram-defined grade II diastolic dysfunction are defined as having an E/e' ratio of > 12 within 12 months of study entry.

4) ESRD patients with confirmed left ventricular hypertrophy (LVH)

Patients with LVH are defined as having left ventricular wall thickness > 1.2 cm confirmed by echocardiogram within 12 months of study entry.

#### **8.5.6 Safety Analyses**

Lokelma-induced hypokalemia will be evaluated based on the total number of hypokalemic events defined as PiccoloPOCT or laboratory-measured K+ of < 3.5 mEq/L.

The incidence of dialysis-related hypokalemia, hypomagnesemia, hypophosphatemia, and low calcium will be evaluated based on the number of events promptly prior to the termination of dialysis where a PiccoloPOCT measurement of K+ is < 2.0 mEq/L OR Ca++ is < 7.0 mEq/L, OR Mg++ is < 2.0 mg/dl, OR a PO4 level is < 3.0 mEq/L. All episodes where a specific electrolyte falls below the above listed threshold will be considered an “event” for that electrolyte. The total number of “events” will be recorded during the 8-week Treatment Phase-1 and the 8-week Treatment Phase-2 cross-over periods and compared between the treatments.

Safety will also be assessed in terms of the frequency of AEs, SAEs, and withdrawals due to AEs, with focus on treatment-related events. Appropriate summaries of these data will be presented by treatment group and/or study period.

Adverse events will be coded using the Medical Dictionary for Regulatory Activities (MedDRA) system organ class (SOC) and preferred term (PT). A treatment-emergent AE

(TEAE) is defined as an AE with the start date on or after the first dose date and up to (and including) 14 days after the last dose date in each of study periods when patients received 3K Bath with Lokelma. However, when patients received 2K Bath without Lokelma, A treatment-emergent AE (TEAE) is defined as an AE with the start date on or after the first visit date and up to (and including) 14 days after the last visit date in each of study periods. Only TEAEs will be included in table summaries.

The number and percentage of participants experiencing AEs, SAEs, AEs that led to withdrawal, AEs that led to death, and the number of such events, will be summarised by SOC, PT, and treatment group and study period. The number and percentage of participants experiencing AEs will further be summarised by intensity and will be presented with the number of events at each level of intensity.

Additionally, the number and percentage of participants with AEs leading to discontinuation of Lokelma will be presented by SOC and PT, and the number and percentage of participants with any AE will be presented by SOC, PT, and relationship to Lokelma as assessed by the investigator. Each of these summaries will also include the number of events.

All AEs, SAEs, AEs that led to withdrawal or death and treatment-related AEs will be included in per-patient listings.

Clinical safety laboratory assessments will be summarised and listed. Shift tables will be provided for select tests, where shift from screening baseline to the worst value within each of study periods will be summarised. Laboratory data outside the reference ranges will be indicated in all listings.

All safety analyses will be performed on the Safety Set. In general, safety assessments will be reported descriptively by treatment group and/or study period. Full details on safety analyses will be provided in the SAP.

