
To evaluate whether the use of Lokelma during periods when patients are receiving a 3.0 K+/2.5 Ca++ bath is associated with hypokalemic events defined as K+ <3.5 mEq/L.
	
 
➤ Total number of hypokalemic events defined as Piccolo Point of Care Testing (POCT) or laboratory-measured K+ of < 3.5 mEq/L.
 

Safety Objective #2: Incidence of Dialysis-related Hypokalemia, Hypomagnesemia, Hypophosphatemia, or Low Calcium	Safety Outcome Measure:

To determine the levels of K+, Mg++, calcium and PO4 during dialysis (measured promptly prior to the termination of dialysis) during experimental treatment [2] compared to standard treatment [3].
 
Note: Each electrolyte is its own "safety" objective independently.
	
➤ Number of events (measured promptly prior to the termination of dialysis) where a Piccolo POCT measurement of K+ is < 3.5 mEq/L OR Ca++ is < 7.0 mEq/L, OR Mg++ is < 2.0 mg/dl OR a PO4 level is <3.0 mEq/L.
 
All episodes where a specific electrolyte falls below the above listed threshold will be considered an "event" for that electrolyte. The total number of "events" will be recorded during the 8-week Treatment Phase-1 and the 8-week Treatment Phase-2 cross-over periods.

Safety Objective #3: Adverse Experiences
	
Safety Outcome Measure:

To evaluate the safety and tolerability of the experimental treatment [2] compared to standard treatment [3] based on the frequency of reported adverse experiences.
	
➤ Frequencies of AEs, SAEs, and withdrawals due to AEs, with focus on treatment-related events.

Exploratory Objectives:
	
Exploratory Outcome Measures:

1) To evaluate the relationship between protein-bound uremic toxins (PBUTs) and atrial fibrillation rates. PBUTs such as indoxyl sulfate (IS) and p-Cresol sulfate (PCS) can induce atrial fibrillation (Aoki et al. 2015; Tang et al. 2015).
	
➤ Correlation between PBUTs (IS, PCS, and ADMA) and the frequency of atrial fibrillation events.

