
2) To determine whether the levels of K+, Mg++, calcium and PO4 (measured promptly prior to the termination of dialysis) correlate with the incidence of clinical events, including intradialytic hypotension, muscle cramping, and cardiac events (defined as atrial fibrillation, bradycardia, ventricular tachycardia, and asystole). We will also evaluate whether the 3.0 K+ dialysate reduces the rates of these clinical events.
	
➤ Correlation between electrolyte levels and clinical events (intradialytic hypotension, muscle cramping, and cardiac events).
 
➤ Correlation between electrolytes falling below threshold levels (Ca++ < 7.0 mEq/L, PO4 levels <3.0 mEq/L, Mg++ < 2.0 mg/dl, and K+ of < 3.5 mEq/L) and cardiac events (defined as atrial fibrillation, bradycardia, ventricular tachycardia, or asystole).

Abbreviations: ADMA=asymmetric dimethylarginine; AE=adverse event; CSCA=clinically significant cardiac arrhythmia; IS=indoxyl sulfate; PBUT= protein-bound uremic toxin; PCS=p-Cresol sulfate; SAE=serious adverse event

[1] Atrial fibrillation will be defined as irregular heart rhythms and irregular R-R intervals in the absence of definable P waves for a minimum of 6 minutes. Each atrial fibrillation event will be adjudicated and validated as a true atrial fibrillation event by a central cardiologist who is blinded to dialysate K+ content.

[2] Experimental treatment (8 weeks): hemodialysis using 3.0K+/2.5 Ca++ dialysate bath, with sodium zirconium cyclosilicate (Lokelma®) supplementation on off-treatment days

[3] Standard treatment (8 weeks): hemodialysis using 2.0K+/2.5 Ca++ dialysate bath, without sodium zirconium cyclosilicate (Lokelma®) supplementation

[4] CSCA events are defined as follows:

- Bradycardia: Heart rate of ≤ 40 beats per minute (BPM) for a minimum duration of 6 seconds.

- Ventricular Tachycardia: Regular tachy-arrhythmia of  $\geq 130$  BPM for a minimum duration of 30 seconds
- Asystole: Absence of detectable ventricular conduction for a minimum of 3 seconds

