## 2.3 Safety Objectives

Safety Objective #1: Lokelma-Induced Hypokalemia	Safety Outcome Measure:
To evaluate whether the use of oral sodium zirconium cyclosilicate (Lokelma ® ) during periods when patients are receiving a 3.0 K + /2.5 Ca ++ dialysate bath is associated with hypokalemic events defined as K + <3.5 mEq/L.	➤ Total number of hypokalemic events defined as Piccolo POCT or laboratory-measured K + of < 3.5 mEq/L.
Safety Objective #2: Incidence of Dialysis-related Hypokalemia, Hypomagnesemia, Hypophosphatemia, or Low Calcium	Safety Outcome Measure:
To determine the levels of K + , Mg ++ , calcium and PO 4 during dialysis (measured promptly prior to the termination of dialysis) during experimental treatment [2] compared to standard treatment [3]. Note: Each electrolyte is its own "safety" objective independently.	➤ Number of events (measured promptly prior to the termination of dialysis) where a Piccolo POCT measurement of K + is < 3.5 mEq/L OR Ca ++ is < 7.0 mEq/L, OR Mg ++ is < 2.0 mg/dl, OR a PO 4 level is <3.0 mEq/L. All episodes where a specific electrolyte falls below the above listed threshold will be considered an "event" for that electrolyte. The total number of "events" will be recorded during the 8-week Treatment Phase-1 and the 8-week Treatment Phase-2 cross-over periods.
Safety Objective #3: Adverse Experiences	Safety Outcome Measure:
To evaluate the safety and tolerability of the experimental treatment [2] compared to standard treatment [3] based on the frequency of reported adverse experiences.	➤ Frequencies of AEs, SAEs, and withdrawals due to AEs, with focus on treatment-related events.

Abbreviations: AE=adverse event; CSCA=clinically significant cardiac arrhythmia; SAE=serious adverse event

[2] Experimental treatment (8 weeks): hemodialysis using 3.0K+/2.5 Ca++ dialysate bath, with sodium zirconium cyclosilicate (Lokelma®) supplementation on off-treatment days

[3] Standard treatment (8 weeks): hemodialysis using 2.0K+/2.5 Ca++ dialysate bath, without sodium zirconium cyclosilicate (Lokelma®) supplementation

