**Table 1 Study Plan and Schedule of Assessments**

Study Period / Visit	Screening	ILR Insertion by EP cardiologist	Baseline/ Randomization	New Dialysate Accommodation Period 1	Treatment Phase 1	Cross-over	New Dialysate Accommodation Period 2	Treatment Phase 2	ILR Removal by EP cardiologist	End of Study	Reference to Protocol Section
Study Week (Wk) [* , ** or ***]	-4 to -3**	-2*	1**	1 & 2**	3 to 10**	11**	11 & 12**	13 to 20**	21-22*	22-23***	
Study Day (D)	-28 to -15	-14	1	1 to 14	15 to 70	71	71 to 84	85 to 140	Between D141 and D155	Within 1 to 14 days after ILR Removal	
Pregnancy Test for Females of Childbearing Potential	X										

Abbreviations: AE=adverse event; Ca=calcium; ECG=electrocardiogram; EP=electrophysiologist; ILR=insertable loop recorder; K=potassium; Mg++=magnesium; PBUTs=protein-bound uremic toxins [including p-Cresol sulfate [PCS], indoxyl sulfate, and asymmetric dimethylarginine [ADMA)]; SAE=serious adverse event

\*Performed on any day. (Note: ILR placement needs to be one week prior to baseline, which starts on Mondays or Tuesdays after each long dialysis weekend.)

\*\*Performed weekly, on Mondays or Tuesdays after each long dialysis weekend. (Note: Screening ICF can be obtained on any dialysis day, but all other procedures need to be performed on Monday or Tuesdays after the long dialysis weekend. Additionally, consenting may be conducted several weeks prior to other study procedures depending on the need for a prohibited medication washout or whether the consenting process occurred on a day other than the Monday or Tuesday after the long dialysis weekend.)

\*\*\*Performed on any dialysis day

[1] K+ Piccolo POCT (utilizing full renal panel) are performed pre-dialysis, on a Monday or Tuesday after the long dialysis weekend, twice during the Screening period, and weekly during the treatment period (both 2-week accommodation periods and 8-week Treatment phases). Note: K+ Piccolo POCT may be performed several weeks after consenting depending on the need for a prohibited medication washout or whether the consenting process occurred on a day other than the Monday or Tuesday after the long dialysis weekend.

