## 5.2 Safety assessments

### 5.2.1 Laboratory safety assessments

Blood samples for determination of select clinical chemistry parameters will be collected and analyzed as indicated in the Study Plan (see [Table 1](#)).

As part of the safety objectives of the study, the number of hypokalemic events defined as Piccolo POCT or laboratory-measured  $K^+$  of < 3.5 mEq/L, and the number of events of pre- or post-dialysis  $Ca^{++}$  < 2.5  $Ca^{++}$  mEq/L,  $PO_4$  levels <3.0 mEq/L and  $Mg^{++}$  < 2.0 mg/dL will be evaluated and compared between the two treatments (experimental vs standard); see [Section 2.3](#).

All Piccolo POCT measurements will be completed locally. The Piccolo POCT device and methodology are described in [Section 8](#), and the blood draws, including sample tubes and volumes collected are detailed in [Section 4.2.1](#). In addition, the following laboratory variables will be measured at the site as part of the Piccolo POCT renal panel:

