#### **8.4.5 Exploratory Efficacy Endpoint #2: Correlation Between Electrolytes and Clinical Events**

The following correlations will be explored:

- Correlation between electrolyte levels and clinical events (intradialytic hypotension, muscle cramping, and cardiac arrhythmias).
- Correlation between electrolytes falling below threshold levels (Ca++ < 7.0 mEq/L, PO4 levels <3.0 mEq/L, Mg++< 2.0 mg/dl, and K+ of < 3.5 mEq/L) and clinical events (cardiac arrhythmias).

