#### **8.4.7 Safety Endpoint #2: Incidence of Dialysis-related Hypokalemia, Hypomagnesemia, Hypophosphatemia, or Low Calcium**

This endpoint is defined as the number of events promptly prior to the termination of dialysis where a Piccolo POCT measurement of  $K^+$  is  $< 2.0$  mEq/L OR  $Ca^{++}$  is  $< 7.0$  mEq/L, OR  $Mg^{++}$  is  $< 2.0$  mg/dl OR a  $PO_4$  level is  $< 3.0$  mEq/L.

All episodes where a specific electrolyte falls below the above listed threshold will be considered an “event” for that electrolyte. The total number of “events” will be recorded during the 8-week Treatment Phase-1 and the 8-week Treatment Phase-2 cross-over periods. Each electrolyte will be its own “safety” objective independently.

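### Safety endpoint #2 is printed with two potassium and two calcium cut-offs, and its 7.0 mEq/L calcium cut-off would flag nearly every reading

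*Protocol*

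**What the plan says.** Safety endpoint #2 is defined in four places in the protocol.

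- Synopsis, Safety Objective #2: an event is a Piccolo "measurement of K + is < 3.5 mEq/L OR Ca ++ is < 7.0 mEq/L".
- Section 2.3 repeats this: "Piccolo POCT measurement of K + is < 3.5 mEq/L OR Ca ++ is < 7.0 mEq/L".
- Section 8.4.7 opens with "This endpoint is defined as the number of events promptly prior to the termination of dialysis where a Piccolo POCT measurement of" and then sets potassium below 2.0 mEq/L and calcium below 7.0 mEq/L.
- Section 8.5.6 agrees with 8.4.7: "measurement of K + is < 2.0 mEq/L OR Ca ++ is < 7.0 mEq/L". It adds that the totals over the two 8-week phases are to be compared between the treatments.

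Section 5.2.1 describes the same safety objective and points to 2.3 as its source. It refers to "the number of events of pre- or post-dialysis" calcium below 2.5 mEq/L, followed by phosphate and magnesium limits that match the other sections.

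The 7.0 mEq/L calcium value is used again in exploratory endpoint #2. Section 8.4.5 has "Correlation between electrolytes falling below threshold levels (Ca ++ < 7.0 mEq/L", and the synopsis exploratory objectives and section 2.4 carry the same value.

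**The concern.** An endpoint with two potassium cut-offs, split two sections against two, has no single definition to program. Sections 8.4.7 and 8.5.6 contradict the outcome measure given in the synopsis and 2.3, and nothing in the protocol says which governs. Section 5.2.1 adds a second calcium cut-off and a wider sampling window.

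The calcium problem goes beyond inconsistency. If almost every reading falls below the cut-off, the event count measures how many samples were drawn, not how often calcium was low. Such a count cannot show a difference between treatments, and an indicator that is nearly always positive cannot be correlated with cardiac events.

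The trial is open-label and analysed by the sponsor or its representatives (section 8.1). If the cut-offs are settled after readings have been seen, the choice is exposed to selection.

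**Working it through.** **1. The passages side by side**

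| Place | Potassium (endpoint #2) | Calcium | Sampling time |
|---|---|---|---|
| Synopsis, Safety Objective #2 | < 3.5 mEq/L | < 7.0 mEq/L | before dialysis end |
| 2.3 | < 3.5 mEq/L | < 7.0 mEq/L | before dialysis end |
| 8.4.7 | < 2.0 mEq/L | < 7.0 mEq/L | before dialysis end |
| 8.5.6 | < 2.0 mEq/L | < 7.0 mEq/L | before dialysis end |
| 5.2.1 (cites 2.3) | not stated | < 2.5 mEq/L | pre- or post-dialysis |

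Section 5.2.1 also gives potassium < 3.5 mEq/L, but for the hypokalaemic events of safety endpoint #1. The potassium conflict in endpoint #2 is therefore about the value only, not the timing.

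**2. Calcium units**

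Calcium has atomic mass 40.08 and valence 2, so 1 mEq/L = 40.08/2/10 = 2.004 mg/dL = 0.5 mmol/L.

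- 7.0 mEq/L = 7.0 × 2.004 = 14.03 mg/dL = 3.5 mmol/L
- 2.5 mEq/L = 2.5 × 2.004 = 5.01 mg/dL = 1.25 mmol/L

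**3. Share of calcium readings flagged**

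The protocol gives no distributions and does not say whether calcium is total or ionised. The means and SDs here are assumptions, with a normal model.

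*Total calcium, means 8.0–10.5 mg/dL, SD 0.5–1.2:*

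- Smallest share below 7.0 mEq/L: Φ((14.03 − 10.5)/1.2) = 0.9984, so 99.8–100% are flagged.
- Largest share below 2.5 mEq/L: Φ((5.01 − 8.0)/1.2) = 0.0064, so 0–0.6% are flagged.

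*Ionised calcium, means 1.05–1.30 mmol/L, SD 0.08–0.12:*

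- Below 7.0 mEq/L (3.5 mmol/L): 100% everywhere.
- Below 2.5 mEq/L (1.25 mmol/L): from Φ((1.25 − 1.30)/0.08) = 0.266 to Φ((1.25 − 1.05)/0.08) = 0.994, so 27–99%.

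**4. Share of end-of-dialysis potassium readings flagged (assumed distributions)**

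| Assumed grid | < 3.5 mEq/L | < 2.0 mEq/L |
|---|---|---|
| Means 3.0–4.0, SD 0.4–0.74 | 11–89% | 0–9% |
| Means 2.5–4.0, SD 0.4–0.9 | 11–99% | 0–29% |

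The two cut-offs come closest on the wider grid at mean 2.5, SD 0.9: Φ((3.5 − 2.5)/0.9) = 0.867 against Φ((2.0 − 2.5)/0.9) = 0.289, a ratio of 3.0. At mean 2.8, SD 0.74 the ratio is 0.828/0.140 = 5.9.

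**5. Scale**

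With 88 randomised patients and 8 weekly readings per phase, there are at most 88 × 8 = 704 end-of-dialysis readings per treatment. On the wider grid:

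- < 3.5 mEq/L: 0.1056 × 704 = 74 to 0.994 × 704 = 700 events
- < 2.0 mEq/L: 0 to 0.289 × 704 = about 204 events

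704 is a ceiling. The actual size of the Safety Analysis Set cannot be derived from the protocol.

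**6. Sampling time**

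The weekly pre-dialysis potassium test is also a full panel (Table 1, footnote 1: "Piccolo POCT (utilizing full renal panel) are performed pre-dialysis"), and Table 2 shows that the panel includes calcium and phosphorus. The post-dialysis draw in section 4.2.1 is the one taken before dialysis ends. The wording in 5.2.1 therefore adds the pre-dialysis readings and takes eligible readings from 8 to 8 + 8 = 16 per patient per treatment. Magnesium is scheduled only before dialysis end (Table 1, footnote 4).

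**The case against.** The strongest case on the other side concerns weight. Low potassium is covered elsewhere: safety endpoint #1 counts readings below 3.5 mEq/L, 5.2.1 compares that count between treatments, and secondary efficacy endpoint #2 compares pre- and post-dialysis potassium outside 4.0–5.5 mEq/L. Section 8.5.6 also calls for laboratory summaries and listings that mark values outside the reference range, with shift tables for select tests, so a truly low calcium would still be visible. Safety is in general reported descriptively, and full details are left to the SAP. All of this stands, and it keeps the point from being graded higher.

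The timing phrase in 5.2.1 stands directly before calcium and may not extend to phosphate and magnesium. That is fair. The conflict is certain for calcium, possible for phosphate, and of no practical effect for magnesium, which has one scheduled sampling time.

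The potassium shares rest on assumed distributions, and their ranges across the grid overlap. That is also true. Within any single distribution on the grid, however, the two cut-offs differ at least threefold, and the contradiction itself needs no distribution.

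Deferral to the SAP does not answer the point. The protocol states the values, and they conflict. A SAP can only pick one and depart from the other.

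**Conclusion.** The concern holds and should be fixed. The potassium split, the second calcium cut-off and the wider calcium sampling time are direct contradictions within the current protocol and need no assumptions. The calcium unit problem follows from conversion: 7.0 mEq/L is 14.0 mg/dL, and at least 99.8% of readings fall below it across the assumed range, whether calcium is total or ionised. As printed, the calcium comparison promised in 8.5.6 is uninformative, and so is the calcium indicator in exploratory endpoint #2. The 2.5 mEq/L value in 5.2.1 behaves quite differently depending on the form of calcium: 0–0.6% flagged if total, 27–99% if ionised.

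The consequence is confined to safety endpoint #2 and one exploratory correlation. The readings are collected either way, so the counts can be produced correctly once the definitions are settled. No efficacy conclusion is affected.

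**What to change.** Before any outcome data are reviewed, reconcile the synopsis and sections 2.3, 5.2.1, 8.4.7 and 8.5.6 to:

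- one sponsor-confirmed potassium cut-off for endpoint #2;
- one calcium cut-off, in the unit and form (total or ionised) that the analyser reports;
- one stated sampling time for calcium, phosphate and magnesium.

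Carry the calcium correction into the synopsis exploratory objectives and sections 2.4 and 8.4.5. Which values are right is for the sponsor to confirm; none is proposed here.

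Two neighbouring details can be checked in the same edit. Phosphate is also given in mEq/L, where 3.0 corresponds to about 3.1 to 9.3 mg/dL of phosphorus depending on the valence taken (3 to 1). Magnesium is listed as a Piccolo measurement although Table 1 and section 4.2.1 send it to the local laboratory.

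The cost is protocol and SAP wording only. All the readings are already scheduled.
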